1. SYNOPSIS

Name of Sponsor/Company: ImmunoGen, Inc.		
Name of Investigational Product: IMGC936		
Name of Active Ingredient: IMGC936		
Protocol Number: IMGC936-0901	Phase: Phase 1/2	Country: United States

Title of Study: A Phase 1/2, First-in-Human, Open-Label, Dose-Escalation and Expansion Study of IMGC936 (Anti-ADAM9 Antibody Drug Conjugate) in Patients with Advanced Solid Tumors

Study center(s): The study will be conducted globally at approximately 26 centers.

Objectives:

Dose Escalation Phase

Primary:

 To assess safety and tolerability, including dose-limiting toxicities (DLTs), maximum tolerated dose (MTD), or maximum administered dose (MAD; if no MTD is defined), and recommended Phase 2 dose (RP2D) for IMGC936

Secondary:

- To characterize the pharmacokinetics (PK) and immunogenicity of IMGC936
- To describe objective response rate (ORR) and duration of response (DoR) for IMGC936 using Response Evaluation Criteria in Solid Tumors version 1.1 (RECIST v1.1)

Exploratory:

- To explore progression-free survival (PFS)
- To explore potential biomarkers of clinical and/or immunologic response to IMGC936 in blood and tumor tissue
- To explore the relationship between baseline ADAM9 (a disintegrin and metalloprotease domain-containing protein 9) expression and antitumor activity

Dose Expansion Phase

Primary:

To describe ORR for IMGC936 using RECIST v1.1

Secondary:

- To characterize safety and tolerability for IMGC936
- To characterize the PK and immunogenicity of IMGC936
- Describe DoR and PFS

Exploratory:

• To explore potential biomarkers of clinical and/or immunologic response to IMGC936 in blood and tumor tissue

- To explore the relationship between baseline ADAM9 expression and antitumor activity
- To explore ocular primary prophylaxis regimens

Study Design:

This study is a Phase 1/2, first in human, open-label, dose-escalation and expansion study designed to characterize the safety, tolerability, PK, immunogenicity, and preliminary antitumor activity of IMGC936.

Participants with relapsed or refractory, unresectable locally advanced or metastatic solid tumors including non-squamous non-small cell lung cancer (NSCLC), triple-negative breast cancer (TNBC), colorectal cancer (CRC), gastroesophageal cancer, or pancreatic cancer will be enrolled.

Planned treatment for both the Dose Escalation Phase and the Dose Expansion Phase consists of IMGC936 administered via intravenous (IV) infusion on Day 1 of Cycle 1 and every subsequent 21-day cycle thereafter (Schedule A, Appendix 1) or IV infusion on Day 1, Day 8, and Day 15 of Cycle 1 and 2, followed by infusion on Day 1 and Day 8 in Cycle 3 and beyond of a 28-day cycle (Schedule B, Appendix 2). Participants may continue on study drug until disease progression, AE requiring discontinuation, withdrawal of consent, physician decision, or other discontinuation criteria are met (Section 5.4).

Dose Escalation Phase

The Dose Escalation Phase is designed to determine the MTD or MAD, if no MTD is defined, and select an RP2D. Dose escalation follows a conventional 3 + 3 design: successive cohorts of 3 to 6 participants each will be evaluated in sequential escalating doses of single-agent IMGC936.

Up to 72 evaluable participants will be enrolled in Schedule A and Schedule B of the Dose Escalation Phase.

IMGC936 is administered via IV infusion at the assigned dose for each cohort. Infusion duration will vary depending on dose and participant tolerability. Sentinel dosing will be used for the first 2 dose levels. The first administration of IMGC936 (Cycle 1) in participants at the first 2 dose levels of Schedule A dose escalation will be staggered by at least 48 hours.

The DLT evaluation period is 21 days for Schedule A and 28 days for Schedule B.

During the Dose Escalation Phase, at the discretion of the sponsor, any dose escalation cohort at a dose level not exceeding the MTD may be expanded to a maximum of 15 participants for further evaluation of safety, PK, antitumor activity, to facilitate selection of the RP2D. Intermediate dose levels, not exceeding the MTD, may also be explored.

Dose Expansion Phase

The Dose Expansion Phase is designed to explore efficacy of IMGC936 at the RP2D as a single-agent in study participants with relapsed or refractory, unresectable locally advanced or metastatic solid tumors.

Upon completion of the Dose Escalation Phase of the study, following determination of the RP2D, and at the sponsor's discretion, up to 7 expansion cohorts may be opened in tumor types selected from those enrolled in dose escalation.

Up to 39 evaluable participants may be enrolled into each expansion cohort (up to 273 participants).

A futility assessment will be conducted on the first 13 participants (Section 14.1) in each expansion cohort. If there are at least 2 responders out of 13 response-evaluable participants at the first stage, an additional 26 participants may be recruited to that cohort (a total of 39 participants) to further evaluate safety, tolerability, PK, immunogenicity, biomarkers, antitumor activity, and survival of participants who received IMGC936.

The expansion cohorts may test more than 1 dose and/or schedule, not exceeding the MTD.

Tumor specimens for determination of ADAM9 expression via immunohistochemical staining will be collected from all participants and will be assayed at a central laboratory designated by the sponsor. ADAM9 testing results are not required for enrollment.

Dose Escalation and Dose Expansion Phases

During both the Dose Escalation and the Dose Expansion phases of the study, safety and tolerability will be closely followed. Further, PK, immunogenicity, antitumor activity, and survival assessments will occur (Appendix 1 and Appendix 4).

Safety Monitoring:

Dose Escalation Phase

For guiding dose-escalation decisions, DLTs will be defined based on treatment emergent adverse events (TEAEs) or abnormal laboratory values that occur up to study Day 21 of Cycle 1 (Schedule A) or study Day 28 of Cycle 1 (Schedule B). AE severity will be graded according to National Cancer Institute Common Terminology Criteria for Adverse Events version 5.0.

Dose Expansion Phase

Safety will be evaluated continuously and in aggregate in the expansion cohorts (Section 4.3). Safety assessments will be based on all TEAEs and abnormal laboratory values.

Number of participants (planned):

Up to a maximum of 345 participants will be enrolled in the study if all expansion cohorts are fully enrolled

Dose Escalation Phase

Up to 45 evaluable participants may be enrolled in Schedule A depending on results during the study and number of dose levels explored. If Schedule B is explored, up to 27 evaluable participants may be enrolled. This number does not account for replacement of non-evaluable participants or the possibility of expanding an individual dose escalation cohort to a maximum of 15 participants to allow for further evaluation of safety, PK, and antitumor activity at that dose level.

Dose Expansion Phase

Up to 39 evaluable participants may be enrolled in each of the 5-7 expansion cohorts.

Diagnosis and main criteria for inclusion:

The population to be enrolled consists of adults with relapsed or refractory, unresectable locally advanced or metastatic non-squamous NSCLC, TNBC, CRC, gastroesophageal cancer, or pancreatic cancer for whom no therapy with demonstrated clinical benefit is available.

Participants must have good performance status, adequate end organ function, and no serious concurrent illnesses that would increase the risk to the participant or confound study data.

Investigational product, dosage and mode of administration:

IMGC936 is an antibody-drug conjugate that consists of an ADAM9-targeting monoclonal antibody and a tubulin-targeting maytansinoid payload, conjugated. IMGC936 dose will be determined during

dose escalation (range 0.5 to 12 mg/kg) and is administered intravenously by following dosing Schedule A and Schedule B (Appendix 1 and Appendix 2).

Duration of treatment:

Participants may continue on study drug until disease progression, AE requiring discontinuation, withdrawal of consent, physician decision, or other discontinuation criteria are met.

It is expected that enrollment for the Dose Escalation Phase of the study will occur over approximately 24 months. The enrollment for the Dose Expansion Phase will occur over approximately 18 months. The total time for conduct of the trial is expected to be approximately 48 months. These estimates of the timing for study conduct may vary from that observed in the actual conduct of the trial.

Criteria for evaluation:

Dose Escalation Phase and Dose Expansion Phase Assessments

Safety Assessments:

The safety assessment will be based on evaluation of AEs that occur from the time of initiation of administration of study drug through the end of treatment visit (EOTV) or 30 days following the last dose of study drug or until the start of subsequent anticancer therapy (whichever occurs first) and will be determined based on signs, symptoms, physical examination findings, and/or laboratory test results from enrolled participants as appropriate.

Ongoing AEs considered related to study drug will be followed until the event has resolved to baseline grade, the event is assessed by the investigator as stable, initiation of another anticancer therapy, withdrawal of consent, lost to follow-up (LTFU), or death.

Progression of the underlying tumor resulting in hospitalization or death (eg, participant hospitalized for or dies from progressive disease (PD) only, without any other serious adverse event [SAE]) will be documented as a PD outcome and not as an SAE.

Response Assessments:

Tumor assessments will be obtained using computed tomography and/or magnetic resonance imaging scans. Target and non-target lesions will be designated at screening and then evaluated after every other cycle, ie, every 6 weeks (\pm 7 days) on Schedule A and every 8 weeks (\pm 7 days) on Schedule B while on study drug.

At each tumor assessment time point, the overall response status will be determined based on assessment of target and non-target lesions as well as appearance of any new lesions. For RECIST v1.1, the overall responses will be categorized as complete response (CR), partial response (PR), stable disease, PD, or not evaluable.

If feasible, participants who discontinue study drug for reasons other than PD, (eg, toxicity, participant request) should continue to undergo tumor assessments every 12 weeks (± 21 days) until evidence of PD, initiation of another anticancer therapy, withdrawal of consent, LTFU, death, or end of study, whichever occurs first.

Pharmacokinetic Assessments:

Serum concentrations of conjugated antibody and total antibody following administration of IMGC936 will be monitored using quantitative validated bioanalytical methods. DM50/51 payload levels will be measured from plasma using a validated liquid chromatography-tandem mass spectrometry assay. Metabolites of IMGC936 may also be evaluated. Single and multiple-dose PK parameters will be derived from serum or plasma concentration versus time data as applicable.

Immunogenicity Assessments:

Antidrug antibodies against IMGC936 will be evaluated using a validated analytical method.

Biomarkers:

Exploratory biomarker assessments are described in the protocol.

Analysis Populations: Two populations will be used for this analysis: the Safety Population and the Response Evaluable Population as defined below.

Safety Population: All participants who received at least one dose of study drug. This population will be used for analyses of safety, PK, and immunogenicity. It will also be used for summary of baseline data and analyses of PFS.

Response Evaluable Population: All participants who received at least one dose of study drug, had baseline measurable or non-measurable disease, and had at least one post-baseline radiographic tumor assessment or discontinued from study drug due to clinical progression or death if no post-baseline tumor assessment. This population will be used for summary of tumor assessment data and analyses of response rates.

Statistical methods:

A separate statistical analysis plan will further describe the details regarding statistical methods and will govern the analysis.

[figure not shown]
Sample Size: The study plans to treat up to approximately 45 participants in dose escalation on Schedule A and up to 27 participants on Schedule B. The sample size is based on a 3 + 3 design with 7 planned dose cohorts of IMGC936. Additional participants may be enrolled if a dose cohort is expanded, participants are replaced, or intermediate dose levels are evaluated.

Each expansion cohort may be expanded independently following an optimal Simon's 2-stage design. If there are at least 2 responders out of 13 response-evaluable participants at the first stage, each may enroll an additional 26 participants to that cohort (a total of 39 participants).

Safety: Treatment-emergent AEs will be summarized by system organ class and preferred term, by relationship to study drugs, and by highest severity. Summaries of laboratory values will display descriptive statistics for numerically quantified laboratory results.

Efficacy: Number and percent of participants with their best overall response will be summarized. Objective response rate will be calculated as the proportion of participants in the Response Evaluable Population achieving a best response of CR or PR. Response rates will be determined using RECIST v1.1. Two-sided 95% exact binomial confidence intervals (CIs) will be calculated around the response rates. Kaplan-Meier methods will be used to estimate duration of response and PFS.

1.1. Study Overview Schema

Abbreviations: FPI: first participant in; PFS: progression-free survival; QXW: every X weeks; RP2D: recommended Phase 2 dose.

Safety assessments occur from the time of initiation of administration of study drug through the End of Treatment Visit or 30 days following the last dose of study drug or until subsequent start of anticancer therapy.

Tumor assessments occur every 2 cycles during treatment (Q6W for Schedule A and Q8W for Schedule B) and Q12W if the participant has discontinued study treatment for reasons other than progressive disease.

Participants enrolled on Schedule B will receive study drug on Days 1, 8, and 15 of a 28-day cycle for the first 2 cycles. On all subsequent cycles (Cycle 3 and beyond), participants will receive study drug on Days 1 and 8 of a 28-day cycle. The 3 + 3 dose escalation will apply to the alternate schedule. The starting dose for Schedule B will be equal to or less than the fractionated total dose of the maximum tolerated dose or maximum administered dose on the original every 3 weeks schedule.

¹ Pharmacokinetics and immunogenicity will be assessed throughout the study (Appendix 4 and Appendix 5).

² Participants who discontinue before progression of disease will be followed for PFS after end of study treatment.

TABLE OF CONTENTS

TITLE PA	AGE	1
SPONSO	R SIGNATURE PAGE	2
INVESTI	IGATOR'S AGREEMENT	3
1.	SYNOPSIS	4
1.1.	Study Overview Schema	9
TABLE (OF CONTENTS	10
LIST OF	ABBREVIATIONS AND DEFINITIONS OF TERMS	17
2.	BACKGROUND INFORMATION	20
2.1.	Rationale for Study	20
2.2.	Disease Background	20
2.2.1.	Non-Squamous Non-Small Cell Lung Cancer	21
2.2.2.	Triple Negative Breast Cancer	21
2.2.3.	Colorectal Cancer	22
2.2.4.	Gastroesophageal Cancer.	22
2.2.5.	Pancreatic Cancer	23
2.3.	IMGC936	23
2.4.	IMGC936 Benefit/Risk in Humans	24
2.5.	Nonclinical Background on IMGC936	24
2.5.1.	IMGC936 Nonclinical Experience	24
2.5.1.1.	IMGC936 Pharmacology	24
2.5.1.2.	IMGC936 Pharmacokinetics and Toxicology	25
2.6.	IMGC936 Dose Selection	26
2.6.1.	Multiples of Monkey Exposure	27
3.	STUDY OBJECTIVES AND PURPOSE	28
3.1.	Dose Escalation Phase	28
3.1.1.	Primary Objective and Endpoints	28
3.1.2.	Secondary Objectives and Endpoints	28
3.1.3.	Exploratory Objectives and Endpoints	28
3.2.	Dose Expansion Phase	28
3.2.1.	Primary Objective and Endpoint	28

		29 March 2022
3.2.2.	Secondary Objectives and Endpoints	29
3.2.3.	Exploratory Objectives and Endpoints	29
4.	INVESTIGATIONAL PLAN	30

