4. INVESTIGATIONAL PLAN

4.1. Overall Study Design and Plan

This study is a Phase 1/2, first-in-human, open-label, dose-escalation and expansion study designed to characterize the safety, tolerability, PK, immunogenicity, and preliminary antitumor activity of IMGC936.

Participants with unresectable, relapsed or refractory, locally advanced or metastatic non-squamous NSCLC, TNBC, CRC, gastroesophageal cancer, or pancreatic cancer will be enrolled globally in approximately 26 centers.

Up to a maximum of 345 participants will be enrolled in the study if all expansion cohorts are fully enrolled.

Each cycle is 21 days for Schedule A and 28 days for Schedule B. IMGC936 is administered via IV infusion at the assigned dose for each cohort. Infusion duration will vary depending on dose and participant tolerability.

Participants may continue on study drug until disease progression, AE requiring discontinuation, withdrawal of consent, physician decision, or other discontinuation criteria are met (Section 5.4).

Participants will be followed for safety throughout the study. Any participant who discontinues study drug should return to the study site for an end of treatment visit (EOTV). The visit should be performed within 30 days following last dose of study drug whenever possible.

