4.5.1. Dose Delays

Participants who experience toxicity should have study drug held pending assessment, management, and resolution of the toxicity. If the toxicity is assessed as unrelated to study drug or does not meet DLT criteria, study drug may be restarted at the previous dose and schedule, after consultation with the medical monitor. The toxicity should have resolved prior to reinstitution of study drug per guidelines outlined in Section 7. Reinstitution of study drug shall be conducted as follows:

• Dose delays of up to 21 days are allowed for participants who experience toxicity. This may include 1 missed dose of IMGC936 on Schedule A and 2 missed doses on Schedule B. The procedures at the originally scheduled missed visit should be performed as soon as possible with study drug reinstituted as if no delay had occurred, picking up at the day where the interruption occurred per the schedule in Appendix 1 and Appendix 2. Participants who have a dose delay of > 21 days may restart study drug with discussion and approval of the sponsor.

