9.9. Radiographic, CT, or MRI Assessments

Tumor assessments are performed according to the schedule in Appendix 1 and Appendix 2. Baseline tumor imaging consists of a CT/MRI scan with contrast, unless medically contraindicated, to document tumor burden. Subsequent tumor assessments on study should use the same imaging modality as that for the baseline assessment.

Tumor assessments are performed every 6 weeks (Q6W; \pm 7 days) on Schedule A and every 8 weeks (Q8W; \pm 7 days) on Schedule B while on study drug then every 12 weeks (Q12W; \pm 21 days). Tumor assessments continue until discontinuation criteria are met. Tumor assessments are performed at EOTV except if prior assessment was \leq 30 days of EOTV and results are available for RECIST v1.1 assessment.

CT or MRI scan of the brain will be performed when clinically indicated (eg, history or suspicion of brain metastases) and repeat brain scans will be performed only if the screening brain scan was positive, or as clinically indicated.

If feasible, participants who discontinue study drug for reasons other than PD (eg, toxicity) should continue to undergo tumor assessments Q12W until evidence of PD, initiation of another anticancer therapy, withdrawal of consent, LTFU, death, or end of study whichever occurs first.

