11. ASSESSMENT OF EFFICACY

11.1. Efficacy Assessments

11.1.1. Disease Response Assessments

Tumor assessments will be obtained using CT and/or MRI scans. Target and non-target lesions will be designated at screening and then evaluated after every other cycle, ie, Q6W (\pm 7 days) on Schedule A and every 8 weeks (Q8W; \pm 7 days) on Schedule B while on study drug (Appendix 1 and Appendix 2). At each tumor assessment time point, the overall response status will be determined based on assessment of target and non target lesions as well as appearance of any new lesions.

If feasible, participants who discontinue study drug for reasons other than PD (eg, toxicity, participant request) should continue to undergo tumor assessments Q12W (\pm 21 days) until evidence of PD, initiation of another anticancer therapy, withdrawal of study consent, LTFU, death, or end of study, whichever occurs first.

• For RECIST v1.1 (Appendix 6), the overall responses will be categorized as CR, PR, SD, PD, or NE. For participants who experience an objective response of CR or PR, responses will be considered unconfirmed until the response has been documented by a subsequent confirmatory scan obtained no less than 4 weeks after the initial scan demonstrating an objective response.

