toxicity is observed during escalation, ocular symptom assessment will occur on Day 1 of each cycle or more frequently if ocular symptoms and signs are observed. Phone-based ocular symptom assessments are acceptable if no clinic visit is scheduled.

- ^h Females of childbearing potential only. Serum pregnancy test is required for eligibility. Subsequent pregnancy tests may use serum or urine. Results must be reviewed before study drug infusion on Day 1 of Cycle 1 and all subsequent cycles. If screening test is performed within 72 hours of first infusion, repeat of the test on Day 1 may be deferred.
- During non-dosing visits (eg, screening and EOTV), vital signs will be taken at one timepoint. For Cycle 1 Day 1, vitals are measured pre-infusion (within 30 minutes before); 15 and 30 minutes after start of infusion (± 5 minutes); EOI (± 10 minutes); and 2, 4, and 6 hours after EOI (± 10 minutes). For Cycle 2 Day 1 and subsequent cycles, vitals are measured pre-infusion (within 30 minutes before), EOI (± 10 minutes), and 1 hour after EOI (± 10 minutes). Participants in dose escalation cohorts must have vital signs recorded on both dosing and non-dosing days through treatment Cycle 3. Beginning on Cycle 4, vital signs must be recorded on Day 1 of each treatment cycle. Participants in expansion cohorts must have vital signs recorded on Day 1 of each treatment cycle.
- ^j To be obtained pre-infusion. Day 1 laboratory samples can be obtained up to 3 days before infusion. Chemistry and hematology results must be reviewed before study drug administration. See Appendix 3 for assessments. Beginning on Cycle 4, laboratory samples only required on Day 1 of each cycle.
- ^k Tumor markers are obtained as indicated for each specific tumor type, eg, CEA for colorectal cancer and CA19-9 for pancreatic cancer. Repeat collection on Cycle 1 Day 1 if screening collection > 7 days prior.
- Tumor assessments are Q6W (\pm 7 days) while participant is on study drug, then Q12W (\pm 21 days). Assessments continue until discontinuation criteria are met. Tumor assessments are performed at EOTV except if prior assessment was \leq 30 days of EOTV and results are available for RECIST v1.1 assessment.
- ^m Tumor assessments will occur after participant has discontinued study drug Q12W (± 21 days) until evidence of PD, initiation of another anticancer therapy, withdrawal of consent, LTFU, death, or end of study, whichever occurs first.

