- ^j To be obtained pre-infusion. Day 1 laboratory samples can be obtained up to 3 days before infusion. Chemistry and hematology results must be reviewed before study drug administration. See Appendix 3 for assessments.
- ^k Tumor markers are obtained as indicated for each specific tumor type, eg, CEA for colorectal cancer and CA19-9 for pancreatic cancer. Repeat collection on Cycle 1 Day 1 if screening collection > 7 days prior.
- ¹ Tumor assessments are Q8W (± 7 days) while participant is on study drug, then Q12W (± 21 days). Assessments continue until discontinuation criteria are met. Tumor assessments are performed at EOTV except if prior assessment was ≤ 30 days of EOTV and results are available for RECIST v1.1 assessment.
- ^m Tumor assessments will occur after participant has discontinued study drug Q12W (± 21 days) until evidence of PD, initiation of another anticancer therapy, withdrawal of consent, LTFU, death, or end of study, whichever occurs first.
- ⁿ Day 15 dose may be omitted in Cycle 2 if significant ocular events occurred in Cycle 1, at the discretion of the investigator.

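### Tumor scans are defined both by cycle and by calendar; after a dose delay of more than 7 days the two conflict, and neither document says which governs

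*Protocol*

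**What the plan says.** Three places tie scans to cycles and add the week interval as an equivalent. Protocol 1.1 has "Tumor assessments occur every 2 cycles during treatment (Q6W for Schedule A and Q8W for Schedule B". The synopsis has lesions "designated at screening and then evaluated after every other cycle, ie, every 6 weeks". Section 11.1.1 has them "evaluated after every other cycle, ie, Q6W". SAP 3.4.2 adds no rule and sends the reader to the protocol synopsis for the assessment schedule.

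Three other places give the week interval only, with a window of 7 days either side. Section 9.9 begins "Tumor assessments are performed every 6 weeks". The Appendix 1 footnote sets the 6-week interval "while participant is on study drug, then Q12W". The Appendix 2 footnote reads "Tumor assessments are Q8W (± 7 days) while participant is on study drug". The disease-assessment rows in both appendices name no starting date, although the tumor-marker rows just above them count from Cycle 1 Day 1.

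On cycle length, Section 4.1 says "Each cycle is 21 days for Schedule A and 28 days for Schedule B". On delays, Section 4.5.1 allows up to 21 days for toxicity, and longer with sponsor approval. Treatment then resumes "with study drug reinstituted as if no delay had occurred, picking up at the day where the interruption occurred per the schedule" in Appendices 1 and 2. The same section asks for the procedures of a missed visit to be done as soon as possible. It does not mention scans.

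**The concern.** The cycle and week definitions are the same only while every dose is on time. Once a cycle slips, one site can scan at the end of the second cycle and another at Week 6, and each can point to protocol text. The resume-where-interrupted rule refers to the appendices that hold the scan rows, so moving the scan with the cycle is a fair reading.

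Delays are foreseeable and linked to toxicity. Section 7.2 reports ocular events already seen with this drug and requires interruption from Grade 2. Table 7 covers resumption after as long as 28 days. Section 4.1.1 gives fewer ocular and other safety events as a reason for exploring Schedule B, so delay rates may differ by dose and schedule.

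Progression is dated when it is documented. If scan dates follow toxicity, recorded PFS and DoR depend partly on tolerability and on how a site reads the protocol.

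**Working it through.** **1. The plan's own equivalence.** Schedule A: 2 × 21 = 42 days = 6 weeks. Schedule B: 2 × 28 = 56 days = 8 weeks. With no delay the two definitions agree.

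**2. When they part.** Under the cycle reading the interval is two cycles plus the delay. The window ends at 42 + 7 = 49 days (A) or 56 + 7 = 63 days (B).
- 7-day delay: 49 and 63 days, just inside.
- 8-day delay: 50 and 64 days, outside.
- 21-day delay: 63 against 42 days (A) and 77 against 56 days (B), both 14 days past the end of the window.

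**3. Landmark PFS rates.** Assumptions, none of them in the documents: exponential PFS with a 10-week median, so S(t) = 2^(−t/10); every event found by scan; one 21-day delay before the first scan; the site follows cycles. Scans then fall at Weeks 9, 15, 21 and so on instead of 6, 12, 18 (A), and at Weeks 11, 19, 27 and so on instead of 8, 16, 24 (B). The recorded rate at a landmark equals S at the last scan before it. SAP 6.2 names 3 and 6 months; Protocol 14.7.3 names 6 and 12.

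| Schedule, landmark | Last scan, calendar | Last scan, cycle | Rate, calendar | Rate, cycle |
|---|---|---|---|---|
| A, Week 13 | 12 | 9 | 43.5% | 53.6% |
| A, Week 26 | 24 | 21 | 18.9% | 23.3% |
| A, Week 52 | 48 | 51 | 3.6% | 2.9% |
| B, Week 13 | 8 | 11 | 57.4% | 46.7% |
| B, Week 26 | 24 | 19 | 18.9% | 26.8% |
| B, Week 52 | 48 | 51 | 3.6% | 2.9% |

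These are rates in delayed participants. If a share f of a cohort is delayed, the Week 13 rate moves by +10.1f points (A) or −10.7f points (B). For f of 20%, 30% and 50% that is about 2, 3 and 5 points, up on A and down on B.

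**4. Average date of recorded progression.** On a calendar grid with interval w the mean recorded time is w/(1 − S(w)). With the first scan moved to w + 3 weeks it is (w + 3) + S(w + 3) × w/(1 − S(w)).
- A: 6/(1 − 0.660) = 17.63 weeks; 9 + 0.536 × 17.63 = 18.45 weeks. Difference 0.82 weeks, or 5.7 days.
- B: 8/(1 − 0.574) = 18.79 weeks; 11 + 0.467 × 18.79 = 19.77 weeks. Difference 0.97 weeks, or 6.8 days.

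A simulation of 200,000 exponential times per scenario, with true medians of 2 to 6 months, gave 2.3 to 6.4 days (A) and 2.8 to 7.7 days (B) for one early delay. With a 21-day delay in every scan interval it gave 11.1 to 12.5 days (A) and 11.3 to 13.2 days (B). The mean rises in every scenario, but individual dates go both ways. On Schedule A a progression at Week 7 is dated Week 9 under cycles and Week 12 under the calendar, while one at Week 5 is dated Week 9 and Week 6. After one early delay, 24% to 45% of progressions are dated earlier. With a 3-month true median, the recorded Schedule A median falls from 126 to 105 days.

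**5. The missed-scan censoring rule.** SAP Table 2 censors an event after two or more missed scans, put into practice as event date − last scan date + 1 ≥ 105 days.
- A, one missed scan, calendar: 84 + 1 = 85, not censored. With both scans at opposite ends of their windows: 84 + 14 + 1 = 99, still not censored.
- A, one missed scan plus a 21-day delay, cycle reading: 105 + 1 = 106, censored.

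So under the cycle reading a Schedule A progression can be censored after one missed scan, and only in participants whose dosing was held. SAP 6.1.4 applies the same rule to DoR. On Schedule B one missed scan reaches the threshold without any delay (112 + 1 = 113); that is a separate matter.

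**The case against.** The strongest reply is that the protocol already means the calendar. Every cycle phrase is followed at once by its week interval, and the 7-day window attaches to weeks. Section 9.9 and the two schedules of events, from which sites work, never mention cycles for scans, while ophthalmic examinations in the same tables are counted in cycles. Section 4.5.1 is about restarting drug, and its instruction to catch up missed procedures promptly weighs against postponing a scan. This has force: the calendar reading is the better supported one, and under it the added effect is zero. It does not close the gap, because no sentence says that scans stay put when cycles move.

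A reader might infer that PFS is biased upward. The documents and the arithmetic do not support that. It needs the cycle reading to be followed, and even then the direction depends on where the landmark falls on the scan grid: Schedule B falls at Week 13, and both schedules fall slightly at Week 52.

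The inputs are also unfavorable. The full 21 days is assumed, before the first scan. On Schedule A an ocular event that resolves between infusions delays nothing. The delayed shares have no source in the documents, and deaths count on their own date, which dilutes the effect.

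Finally, the stakes are limited. PFS is secondary in expansion and exploratory in escalation, there is no control arm, and the SAP plans no test. At n = 39 and a rate of 43.5%, the 95% half-width is about 1.96 × √(0.435 × 0.565/39) = 16 points, well above a cohort shift of 2 to 5. All of this stands, and it limits the weight of the point.

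**Conclusion.** The point holds as an unresolved conflict in the text with a conditional consequence. Scans carry two definitions that disagree beyond the window after any delay of more than 7 days, by 21 days after a 21-day delay, and neither document ranks them.

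Where sites follow cycles, scan timing depends on toxicity. Progression is then recorded about 6 to 7 days later on average in a participant with one early 21-day delay (10-week exponential median), and the 3- and 6-month rates in delayed participants move by roughly 4 to 11 points, up or down. One missed Schedule A scan can then trigger censoring meant for two. These sizes rest on the assumed median, delay and site behavior; the documents give none of them.

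The effect is on descriptive PFS and DoR and on informal comparisons between doses and schedules with different delay rates. Two further inferences are not supported: that scan timing already follows toxicity across the trial, and that the primary ORR endpoint is affected.

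**What to change.** In the synopsis, Sections 1.1, 9.9 and 11.1.1, and Appendices 1 and 2, state one rule: while on study drug, tumor assessments occur every 6 weeks (Schedule A) or every 8 weeks (Schedule B), within 7 days either side, counted from Cycle 1 Day 1 and not moved for dose delays. Delete the phrases that set scans every two cycles or after every other cycle.

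The cost is amendment wording. It adds no scans beyond the interval already stated. The downside is that some scans will not coincide with a dosing visit. No change to the dose-delay rules is proposed.
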